7.1 Inclusion Criteria

Subjects in whom the subject and study eye meet all of the following criteria are candidates for this study:

1. 22 years of age or older.
2. Eligible for unilateral DCR surgery with stenting for treatment of epiphora secondary to nasolacrimal duct obstruction. Ability to instill post-operative eye drop
3. Signed written, informed consent.
4. Willingness and ability to comply with schedule for follow-up visits and postoperative evaluations.

7.2 Exclusion Criteria

All subjects in whom the subject or study eye meets any of the following criteria will be excluded from the study:

- Subjects less than 22 years of age
- Subjects scheduled for bilateral DCR surgery
- Subjects with known sensitivity to silicone
- Subjects with a current condition that, in the investigator's opinion, would interfere with the treatment.

- Inability to use eye drops
- Subjects with a known sensitivity to required study medications (e.g. antibiotic drops) if an alternative medication is not available.
- Subjects under legal guardianship or who, in the investigator's opinion, lack the mental capacity to provide written informed consent for study participation.

8.0 STUDY DURATION AND EXAMINATION SCHEDULE

8.1 Study Duration

The study duration will be 6 months (+/- 1 month) for all study patients.

8.2 Examination Schedule

The following examination schedule will be followed from screening through the postoperative visits:

- Screening (Day -60 to Day 0 Preoperatively)
- Device implantation operation
- Phone call Assessment at 1 day post op
- Phone call Assessment at 45 days post op (+/- 15 days)
- Day 5-14 postoperatively
- Day 30-120 postoperatively (with stent removal)
- 5-7 month final post-operative exam

The screening visit should be completed anytime within the 60 days prior to the scheduled surgery. Unscheduled visits may be completed at the investigator's discretion or as medically necessary before or after the implant surgery.

All final exam procedures will be completed at the second post-operative study visit.

9.0 STUDY PROCEDURES

Subjects who elect to participate in this study will complete the study as outlined below. Subjects will be randomly assigned to the experimental vs. control stents using a randomized block design with 1:1 allocation to treatment and control. Stents will be provided to the surgical team on the day of surgery by the Study Coordinator. Surgical team, recruitment staff, and scheduling staff will be masked to treatment assignment until day of surgery. All tests and measurements should be obtained in accordance with the procedures specified in this protocol. If it is not possible to perform a measurement or examination due to the individual eye's specific ocular pathology, the reason for not performing the test or measurement should be documented on the source documents.

The investigator may designate one or more surgeon sub-investigators at his/her investigative site. A surgeon sub-investigator may evaluate subjects for the study and perform the Slit Stent II lacrimal stent intubation. Surgeon sub-investigators will be listed on all applicable investigator regulatory documents (including the delegation of responsibilities log) and will complete all sponsor-required training for the study.

For the pre-op and all post op study visits, the Lac-Q Questionnaire will be administered by an interviewer, and the interviewer will record the subject's responses directly onto the corresponding questionnaire CRFs or source documents and calculate the Lac-Q score. For post op visits, the Lac-Q Questionnaire will be given prior to other questionnaires.

For the two post-op study visits, the Quality of Life (QOL) questionnaire (Glasgow Benefit Inventory (GBI)- see Appendix A) and the Patient Stent Tolerance and Irritation Assessment (see Appendix C) will be administered by an interviewer, in this order, and the interviewer will record the subject's responses directly onto the corresponding questionnaire CRFs or source documents and calculate the GBI score.

When multiple questionnaires are given at the same visit, the order shall always be: 1) Lac-Q, 2) GBI QOL, and 3) Patient Stent Tolerance and Irritation Assessment.

9.1 Slit Stent II Intubation Evaluation

Candidates for the Slit Stent II may be identified from the investigator's clinical practice or may be referred by outside ophthalmologists. All screening examination procedures will be performed by the investigator or trained personnel working under the investigator's supervision.

9.1.1 Referring Physicians

Subjects may be referred to the investigator for enrollment in the study. Evaluation of the lacrimal complaint and eligibility for DCR surgery and for the study will be assessed independently by the investigator.

9.1.2 Bilateral and Fellow Eye Treatment

Same day bilateral implantation of the Slit Stent II will not be allowed in the study.

9.1.3 Screening Eye Examination (Day -60 to Operative Day 0)

Informed consent must be signed and dated before any study procedures are performed that are specific for the study and not part of the routine evaluation or examination. A copy of the informed consent must be given to the subject and documented in the source documents. After informed consent is obtained, each potential Slit Stent II candidates will be evaluated in order to determine his/her eligibility for study participation. The complete ophthalmic clinical evaluation will take place before informed consent. Any assessment that is required on the screening CRF which was not completed as part of standard clinical exam will be completed after the consent is

obtained. Demographics and an ocular history, medical history, allergies and current medication list will be obtained. Please refer to the flow chart in **Appendix D** for the schedule of events for each listed study activity. The complete screening eye examination of the operative eye and subject histories will include, where medically possible:

- **Demographics** (Date of birth, gender, ethnicity. Age is calculated from the subject's date of birth and the informed consent date; subjects must be at least 22 years of age at the informed consent date.)
- **Medical history**
- **Medication list** (Baseline medication history should include all current prescribed medications and all routinely taken non-prescription medications)
- **Ocular history**- Baseline ocular history at the screening examination should include known ophthalmic conditions and prior eye surgeries.
- **Lac-Q questionnaire (Appendix B)**
- **Lacrimal system probing/irrigation**
- **Corrected visual acuity and manifest refraction**- Corrected visual acuity is measured in each eye after manifest refraction using the Early Treatment Diabetic Retinopathy Study (ETDRS) charts. The distance from the subject's eyes to the ETDRS chart should be 3 meters. The standard ETDRS chart light box will be used. ETDRS Chart 1 will be used for the Right eye and Chart 2 for the Left Eye. Chart R will be used for manifest refraction. Room illumination will be at highest illumination (Appendix E).
- **Intraocular pressure**- Intraocular pressure measurement is measured by the iCare tonometry method. IOP measurement should be performed after visual acuity measurements.
- **Slit lamp biomicroscopy** of lid margins, puncta, conjunctiva and cornea- Slit lamp biomicroscopy with use of fluorescein should include a complete survey of the lid margins, puncta, conjunctiva and cornea. The Oxford scheme will be used to grade corneal and conjunctival staining. Any abnormalities such as corneal infiltrates and punctate erosions should be documented. The tear lake is measured using a slit lamp by narrowing the slit and shortening it to 1 mm or 0.2 mm, placing the slit light beam on the inferior lid margin tear lake, and using the beam to measure the vertical height of the fluid between the lid margin and the location of the top of the tear lake on the conjunctiva or cornea.

Other optional diagnostic tests may be performed at the investigator's discretion (e.g., dacryoscintigraphy, Jones test, etc.) to further evaluate the subject for nasolacrimal duct obstruction surgery or as dictated by the clinical situation. The results of optional diagnostic tests will be maintained in the source documents but will not be recorded on the CRFs.

9.2 Concomitant Medication

Subjects are permitted to take prescribed or non-prescription medications and supplements before and after the DCR procedure, at the discretion of the investigator. Medications used

during the operative procedure will be documented in the source documents for the operative procedure but will not be captured on the case report forms, unless the medication was used to treat an intraoperative adverse event or complication.

9.3 Stent Intubation Procedure (Operative Day 0)

The staff should confirm that the informed consent form (ICF) for the study has been signed, dated and a copy was given to the subject. The surgical staff is responsible for assuring that any additional surgical consent forms or HIPAA forms required by the clinic or institution are signed before surgery. Subject history and other tests or measurements from the screening examination or that are otherwise dictated by the subject's condition may be performed at the discretion of the investigator, to provide accurate baseline measurements or to determine continuing eligibility for the nasolacrimal duct intubation surgery.

The study statistician will create (via randomized block design) a treatment assignment list and provide it to the study coordinator only. The study coordinator will provide the correct stent at the time of the operation. Type of stent will not be recorded in patient record. Patient will not be told which stent was installed.

9.3.1 Subject Preparation

The subject will be prepared for surgery, and the operated side will be prepped and draped in the surgeon's usual sterile fashion for ophthalmic surgery. The DCR surgical procedure will be performed under standard Anesthesia conditions as per standard clinical care at the University of Michigan. Medications administered perioperatively may include sedation or anesthesia, antibiotics, and other surgical antimicrobials (e.g., povidone iodine) or medications used during any concomitant surgical procedure (e.g., steroids, antimetabolites). Local anesthesia will be performed at the surgeon's discretion based on the subject's clinical condition and surgical plan using the surgeon's standard drug regimen fashion.

9.3.2 Stent Intubation General Surgical Procedure

DCR surgery with stenting will be performed in a standard fashion opening the lacrimal sac, creation of an osteotomy connecting the nose to the lacrimal sac, and placing the stent under direct visualization. There are two techniques: External DCR and Endonasal DCR.

The external DCR involves (1) skin incision over the lacrimal sac, (2) exposure of lacrimal bone, (3) creation of an osteotomy into the nasal cavity using a bone-removal instrument, (4) opening of the lacrimal sac, (5) opening of the nasal mucosa, (6) placement of the lacrimal stent, (7) closure of the mucosa and surgical wound.

The endonasal DCR involves (1) visualizing the middle meatus in the nose, (2) identifying the position of the lacrimal sac (using a canalicular probe or light source), (3) creation of an osteotomy with a bone removal device to expose the lacrimal sac to the nasal cavity, (4) opening of the lacrimal sac, (5) placement of the lacrimal stent.

The selection of the DCR surgical technique will be determined by the surgeon and dictated by the clinical condition and lacrimal duct anatomy and pathology. This study does not aim to assess the efficacy of DCR surgery, and considers DCR surgery to be a well-established and efficacious surgical procedure for the treatment of epiphora secondary to nasolacrimal duct obstruction.

Operative records should be kept during the procedure or dictated postoperatively that describe medications used, the surgical technique for stent placement, concomitant surgical procedures, any operative complications or adverse events, and any planned or anticipated secondary surgical procedures. The position of the stent with respect to the location of central slit position relative to medial canthal interpalpebral function will be recorded on the CRFs. Medications used in conjunction with the surgical procedure will be described in the operative records and will not be recorded on the CRFs. The operative records will be retained in the source documents.

9.3.3 Postoperative Care

Written postoperative instructions will be given to each subject and reviewed prior to discharge. The following postoperative eye drops will be prescribed for the following minimum times:¹

- An antibiotic-steroid combination eye drop (e.g. Tobramycin-Dexamethasone or Neomycin-Polymyxin-Dexamethasone) placed 4 times daily for 2 weeks, then twice daily for 2 weeks, then once daily for at least 2 weeks or until stent removal, as determined by the surgeon.

Additional medications including, but not limited to, erythromycin ointment and bacitracin ointment will be used at the discretion of the operating surgeon. All postoperative eye drop usage will be recorded on the source documents and on the CRFs. Other prescription or nonprescription medications, including pain medications, may be taken as needed throughout the study.

9.4 ***Follow-Up Visits (Day 1 phone call, Day 5-14 Postoperatively, Day 30-60 phone call, Day 30-120 Postoperatively, Month 5-7 Postoperatively)***

A study flow chart summarizing the follow-up examination schedule and required procedures to be performed at each study visit is provided in **Appendix D**. All subjects will be seen for a 1st post-operative visit 5-14 days after the DCR with intubation, for a 2nd post-operative visit at 30-120 days after intubation, and for a final visit at month 5-7 postoperatively, with the exact timing dependent on patient findings and surgeon discretion. Unscheduled visits may be completed at the investigator's discretion or as medically necessary.

During the Day 1 and Day 30-60 phone assessments, the patient will be asked about any

¹ An alternative antibiotic or anti-inflammatory drug and dosage regimen may be used to conform with clinic or hospital formulary or prescribing requirements, with sponsor approval. An example would be neomycin-polymyxin-dexametasone eye drop (i.e. "Maxitrol").

postoperative swelling or pain or other adverse effects. If the patient reports any symptoms that would require a follow-up visit, we will ask the patient to return to the University of Michigan if possible. If this is not possible due to transportation issues, we will have them return to their referring ophthalmologist.

The following procedures will be performed **at the day 5-14 and day 30-120 post-operative visits** unless noted otherwise.

- **Documentation of interim medical, ocular, and medication histories** since previous visit. The ocular history should capture any changes in the study eye since the previous visit; and, any relevant changes to the fellow eye that are necessary to evaluate an adverse event or anomaly in the study eye. The medication history should capture any changes in prescribed medications or routinely taken non-prescription medication since the previous visit.
- **Subjective reports of tearing-** we will capture the subject's report of their tearing symptoms since the surgery procedure
- **Corrected distance visual acuity** - Corrected visual acuity is measured in each eye by the ETDRS chart at 3 meters using the manifest refraction obtained at the previous visit. If there is a 2-line or more reduction in visual acuity from the last corrected visual acuity, a repeat manifest refraction in each eye will be performed.
- **Intraocular pressure-** Intraocular pressure measurement is measured by the ICare tonometry method, performed after visual acuity measurement had been completed.
- **Slit lamp biomicroscopy** (including conjunctiva and cornea), with use of fluorescein- Slit lamp biomicroscopy should include a complete survey of the conjunctiva and cornea, and of the tear lake. The Oxford scheme will be used to grade corneal and conjunctival staining. The tear lake is measured using a slit lamp by narrowing the slit and shortening it to 1 mm or 0.2 mm, placing the slit light beam on the inferior lid margin tear lake, and using the beam to measure the vertical height of the fluid between the lid margin and the location of the top of the tear lake on the conjunctiva or cornea.
- **Visual inspection of stent integrity and slit positioning-** External and slit lamp exam of the medial canthal area and the medial commissure. The presence of the lacrimal stent within the medial commissure, between the puncta, will be documented as (1) present, slit in fissure, (2) present, slit not in fissure, or (3) not present.
- **Lac-Q questionnaire (Appendix B)**
- **Glasgow Benefit Inventory Questionnaire (Appendix A).**
- **Patient Stent Tolerance and Irritation Assessment (Appendix C)**
 - **The 3 questionnaires will always be given in the same order: 1) Lac-Q, 2) GBI, and 3) Stent Tolerance Assessment.**
- **Other diagnostic tests-** Jones I, Jones II or lacrimal irrigation at investigator's discretion
- **Adverse events, complications, visual disturbances-** Visual disturbances are any unexpected, expected, or pre-existing sight related occurrences that are not captured in any of the examinations or measurements, such as nystagmus or diplopia.

Unexpected or new reports of visual disturbances related to the device or surgical procedure should be recorded on the complications/adverse event case report form.

In addition to the above procedures, **at the day 30-120 visit**, we will collect, examine (photo) and culture all stents after retrieval from the nose. Culturing will consist of placing the retrieved stent in a standard container and submitting it to microbiology for culture and sensitivities.

Removal of the stent entails cutting the holding suture in the nose with scissors under direct visualization, with the help of a nasal speculum if needed, cutting the stent itself with scissors once to linearize it, and then pulling the stent out either from the nose or from the puncta using forceps.

Upon stent removal, the surgeon will comment on whether stent removal was technically simple, moderate or difficult (binary). This will be recorded on the CRF.

At the Final Visit, month 5-7, the following procedures will be performed:

- **Documentation of interim medical, ocular, and medication histories** since previous visit. The ocular history should capture any changes in the study eye since the previous visit; and, any relevant changes to the fellow eye that are necessary to evaluate an adverse event or anomaly in the study eye. The medication history should capture any changes in prescribed medications or routinely taken non-prescription medication since the previous visit.
- **Lac-Q questionnaire (Appendix B)**
- **Glasgow Benefit Inventory Questionnaire (Appendix A).**
 - **The 2 questionnaires will always be given in the same order: 1) Lac-Q, 2) GBI.**
- **Corrected distance visual acuity** - Corrected visual acuity is measured in each eye by the ETDRS chart at 3 meters. If there is a 2-line or more reduction in visual acuity from the last corrected visual acuity, a repeat manifest refraction in - each eye will be performed.
- **External exam of the medial canthal area and the medial commissure**
- **Slit lamp biomicroscopy of the puncta, lid margins and ocular surface.** The Oxford scheme will be used to grade corneal and conjunctival staining. The tear lake is measured using a slit lamp by narrowing the slit and shortening it to 1 mm or 0.2 mm, placing the slit light beam on the inferior lid margin tear lake, and using the beam to measure the vertical height of the fluid between the lid margin and the location of the top of the tear lake on the conjunctiva or cornea.
- **Adverse events, complications, visual disturbances-** Visual disturbances are any unexpected, expected, or pre-existing sight related occurrences that are not captured in any of the examinations or measurements, such as nystagmus or diplopia.

Unexpected or new reports of visual disturbances related to the device or surgical procedure should be recorded on the complications/adverse event case report form.

Because of the distances involved, we can anticipate that some patients will not be able to make the trip to Ann Arbor due to distance or transportation issues, especially in the case of successful surgery with symptomatic resolution. In those cases, we will document this matter in the report form and make a phone-call assessment of patient status, which will be reported.

Other optional diagnostic tests such as lacrimal irrigation/ or Jones 1 or Jones 2 tests may be performed at the investigator's discretion to further evaluate the subject's postoperative outcome or as dictated by the clinical situation. These tests and their results will be recorded accordingly on the CRFs.

Extensive effort will be made by telephone and mail to contact subjects who miss a scheduled follow-up visit to arrange a new appointment.

Postoperative observations and adverse events will be documented in the subject's medical records. Complications or adverse events that are observed by the investigator or reported by the subject should be recorded on the CRFs. For all adverse events and complications, a description of the event, date first observed, any action taken, and ultimate outcome will be recorded.

For all adverse effects, sufficient information will be pursued and/or obtained so as to permit 1) an adequate determination of the outcome of the effect (i.e., whether the effect should be classified as a serious adverse effect) and; 2) an assessment of the causal relationship between the adverse effect and the investigational device or, if applicable, the other study treatment or diagnostic product(s). Adverse events present at the end of study will be followed until resolved or the Sponsor Investigator determines no further follow-up for the study is required. Any findings related to the adverse event that are obtained after the final study visit is completed will be documented in the subject's medical records and the relevant findings will be recorded on the adverse event and adverse event summary CRFs.

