9.6 Safety Monitoring

Subjects will be observed closely to detect any adverse events or complications that may have occurred. On the day of treatment and at each follow-up visit, subjects should be asked a non-leading question, such as "How are your eyes?" to determine whether any complications or adverse events might have occurred since the last visit. The presence or absence of adverse

events or complications will be documented. All exam findings, work-up, management, and sequelae relevant to an AE will be recorded on the AE CRF.

Ophthalmic safety will be evaluated by slit lamp biomicroscopy of the operated eye. In the case of an adverse event or complication, these tests, and any others deemed necessary, may be repeated before the next scheduled visit at the investigator's discretion. Appropriate supportive and/or definitive therapy may be administered as required. Any complications or adverse events will be recorded in the medical record/CRF.

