10.5 Outcome Criteria

Complications and adverse events are the primary safety outcomes to be evaluated. All complications and adverse events and their rates of occurrence will be reported. Changes in the subject's symptoms (tearing, irritation) and quality of life as measured by the GBI are the primary effectiveness outcomes.

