All ophthalmic adverse events should be recorded on the adverse event forms in the CRFs. Adverse device effects /events that are determined by the sponsor investigator to be vision-threatening should be considered to be reportable as described below.

Adverse events that occur in association with a device that is used in conjunction with the Slit Stent II will be reported separately.

Postoperative observations that, after sponsor investigator review, are determined to be part of the normal healing process that occurs after the nasolacrimal intubation procedure are not considered to be reportable events.

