11.4 Monitoring

11.4.1 Medical Monitor

An independent Medical Monitor will be appointed to review each Serious Adverse Event. Any Serious Adverse Events will be reported to [name], the sponsor of the study, who will in turn notify the Medical Monitor. The Medical Monitor will review the event, request any additional data if necessary, and make a determination regarding expectedness and relatedness. Also, the Medical Monitor will determine if this safety data increases the risks to subjects on the trial. All non-serious adverse events will also be reviewed by the Medical Monitor on a quarterly basis.

[name] will be responsible for reporting the events to the IRB and the FDA as appropriate. The Medical Monitor review will be maintained in the study records.

The Medical Monitor may meet in person or through a teleconference with other individuals with clinical expertise as needed.

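### Section 9.4 makes relatedness a condition for entering new visual disturbances on the adverse event form, in conflict with the protocol's general recording rules

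*Combined protocol and SAP*

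**What the plan says.** Section 9.4 lists the procedures for the day 5-14 and day 30-120 visits, and then those for the final visit at month 5-7. Both lists have an item covering adverse events, complications and visual disturbances. The item first defines its last term broadly: "Visual disturbances are any unexpected, expected, or pre-existing sight related occurrences that are not captured in any of the examinations or measurements". It then gives the recording instruction: "Unexpected or new reports of visual disturbances related to the device or surgical procedure should be recorded on the complications/adverse event case report form". The wording is the same in both lists.

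Three other recording rules carry no condition about cause:

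- Section 9.4, after the visit lists: "Complications or adverse events that are observed by the investigator or reported by the subject should be recorded on the CRFs".
- Section 9.6: "Any complications or adverse events will be recorded in the medical record/CRF".
- Section 11.3: "All ophthalmic adverse events should be recorded on the adverse event forms in the CRFs". The opening of 11.3 likewise sends observed or reported ophthalmic events to the CRFs.

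Sections 9.4 and 11.3 also ask for enough information on every adverse effect to assess its causal relationship to the device. That is a separate step, taken on an effect already identified.

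Section 10.5 makes complications and adverse events the primary safety outcomes and adds: "All complications and adverse events and their rates of occurrence will be reported". Section 11.4.1 provides independent oversight: "All non-serious adverse events will also be reviewed by the Medical Monitor on a quarterly basis".

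**The concern.** An adverse event rate can be compared between arms only if what gets counted does not depend on an opinion about cause. Normally everything new is recorded, relatedness is noted beside it, and both totals are reported. The visual disturbance sentence reverses that order for one category, because relatedness comes first and the form second.

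A report left off the form would be missing from the rates in Section 10.5. It would also be missing from the Medical Monitor's quarterly review, which can cover only events that were recorded. The study compares a modified device with its parent. Section 11.3 calls the risks identical to those of existing surgery and stenting, and the complication lists in 3.1 and 11.3 name no visual disturbance. An unlisted effect is easy to judge unrelated, yet it is one that such a comparison should be able to detect.

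**Working it through.** The plan gives no figure on this point, so the main check is to follow one case through the rules.

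**Step 1. A test case.** A subject reports new, non-serious double vision at the day 5-14 visit, and the examiner thinks neither the stent nor the operation caused it.

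| Rule | Condition about cause? | Result for this case |
|---|---|---|
| 9.4, visual disturbance sentence | Yes | Not directed to the adverse event form |
| 9.4, general rule | No | CRF, if it counts as an adverse event |
| 9.6 | No | Medical record or CRF |
| 11.3 | No | Adverse event form, if it counts as an ophthalmic adverse event |
| 9.4 and 11.3, causality | Separate step | Assessed once the effect is identified |

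The visit-level sentence and the general rules give different answers.

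**Step 2. Does the text settle it?** Not clearly. The general rules apply once something is an adverse event or complication. The text available gives no general definition of an adverse event, and Section 11.3.1 defines only the unanticipated adverse device effect. The 9.4 item lists adverse events, complications and visual disturbances side by side, so staff could treat the third as distinct until the sentence admits it. The qualifier does no work unless it selects a subset.

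**Step 3. Is the judgement masked?** Section 6.0 describes a single-blind design. Section 9.0 masks the surgical team, recruitment staff and scheduling staff until the day of surgery. Section 9.3 keeps stent type out of the patient record and from the patient. Section 9.4 has the position of the slit graded at the day 5-14 and day 30-120 visits, which can reveal the arm. No masked assessor is named, and no passage says who judges relatedness for visual disturbances. That the examiner may know the arm is therefore an inference, though a fair one.

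**Step 4. What else would catch the report?** Interim ocular history, taken at all three visits, is meant to note changes in the study eye. However, no passage carries interim history into the safety rates or the Medical Monitor's review, and Section 10.4 lists only histories from screening. Serious events go to the Medical Monitor under 11.4.1, and vision-threatening adverse events have their own route under 11.3.1.1. What remains exposed is non-serious disturbances that do not threaten vision.

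**Step 5. Scale.** Section 10.1 gives 25 subjects per arm. One omitted subject changes an arm's rate by 1/25 = 0.04, or 4 percentage points.

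For illustration only, let both arms have the same true rate p, and let a fraction r1 be recorded in one arm and r2 in the other. The false difference is p × (r1 − r2). Every p and r below is an assumption.

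| Assumed p | r1 = 0.75, r2 = 0.50 | r1 = 1.00, r2 = 0.50 |
|---|---|---|
| 4% (1 in 25) | 0.04 × 0.25 = 1 point | 0.04 × 0.50 = 2 points |
| 10% | 0.10 × 0.25 = 2.5 points | 0.10 × 0.50 = 5 points |
| 30% | 0.30 × 0.25 = 7.5 points | 0.30 × 0.50 = 15 points |

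Swapping r1 and r2 reverses the sign. Equal filtering gives no false difference but understates both rates: with p = 20% and r = 0.50 in each arm, both record 10%. For comparison, Section 10.1 puts the maximum half-width of the interval for a difference of two proportions at 0.27, or 27 points.

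**The case against.** A reader might infer that a visual disturbance reaches the form *only* if judged related, so that an unmasked causality call decides what enters the primary safety rates. The documents do not support this. The sentence says that related disturbances should be recorded; it never says that others stay off. Section 11.3 independently sends every ophthalmic adverse event to the adverse event forms, so new double vision that counts as one must be recorded whatever its cause. A filter on the safety rates is not established.

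Nor do the documents support saying that a report left off the form has nowhere else to go, since interim ocular history can hold it. Blurring from a watery or sticky eye has its own Lac-Q item, and acuity is measured at all three visits, which narrows the category further. They also give no basis for quoting a particular bias: there is no visual disturbance rate, and no evidence that relatedness would be judged differently by arm. At low rates the effect would be a fraction of a subject, well inside the plan's own margin of error. Imperfect masking is a feature of the whole trial, not of this sentence.

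All of that stands, and it limits the point. It does not remove the contradiction. The narrow sentence is the visit-level instruction specific to visual disturbances, it appears twice, and its qualifier departs from the general rules.

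**Conclusion.** The point holds as a contradiction between a visit-level instruction and the general recording rules. If staff follow the narrow sentence, a relatedness judgement by someone who may know the arm could drop non-serious visual disturbances from the primary safety rates and from the quarterly review. If they follow Section 11.3, ophthalmic adverse events are not lost on grounds of cause.

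The affected category is small. The only size that follows from the documents is 4 percentage points per omitted subject in an arm of 25. The frequency of such omissions, and the direction and size of any difference between arms, cannot be derived.

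The conclusion assumes that the case report forms, which are not in the documents, do not already resolve the matter, and that some examiners know or can infer the arm. It deserves correction because reports left off the form may not be recoverable at analysis.

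**What to change.** In both places in Section 9.4 where the sentence appears, delete the qualifier limiting it to disturbances attributed to the stent or the operation. Every new or unexpected visual disturbance then goes on the complications and adverse event form. Record relatedness as a separate field on that form, assessed without knowledge of the arm where feasible. In Section 10.5.1 and the SAP, state that all events are tabulated by arm, with related events shown as a subset.

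This brings the visit instructions into line with the general rules in 9.4 and 11.3 and with the rates promised in 10.5. The cost is one phrase deleted in two places, a check that the form has the field, and a few more adverse event lines, some unrelated. No clinical management changes.
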